2.2. Study design

This study is a single-centre, double-masked, randomised, two-arm, parallel-group interventional study comparing the effects of omega-3 EFA oral supplements with olive oil (placebo) supplements over six months. Participants will be randomised according to a 1:1 allocation ratio to omega-3 PUFA supplements (defined below) or an olive oil (placebo) supplement.

The primary outcome measure is the change in central corneal nerve fibre length (CNFL) from baseline (Day 1); the primary analysis endpoint is Day 180 (six months).

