2.4. Study population and entry criteria

2.4.1. Number of participants

A total of 50 patients will be randomised over the study duration.

Given a two-arm parallel design, with the pre-specified primary outcome of CNFL (taken as a continuous measure), for 80% power at a confidence level of 95%, using an estimated true difference between intervention arms of 2.9 units, mm/mm² (Chinnery *et al.*, 2017b), based on an expected standard deviation of 3.2 units, the required sample size is 21 participants per group. To allow for 15% participant attrition, the sample size within each group will be increased by this amount, giving a need to recruit a total of 25 participants in each interventions arm (n=50 for the trial).

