8.1.3. Methods of analysis

The primary outcome measure is the change in central corneal nerve fibre length (CNFL) from baseline (Day 1); the primary analysis endpoint is Day 180 (six months).

A range of secondary outcome measures, including safety outcomes, will be investigated (as detailed in Section 5.1).

For continuous outcome measures, a repeated measures model will be used to assess for differences in the post-treatment means between groups (i.e., the main effect of group) at each time point, with the baseline (Day 1) values used as a covariate. For binary and categorical outcome measures, an ordered logistical regression model will be used. For all analyses, an alpha level of 0.05 will be adopted for statistical significance. Unless otherwise specified, data will be expressed as mean plus/minus standard deviation.

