To evaluate the effects of a six-month supplementation period with oral long-chain omega-3 PUFA supplements on peripheral nerve health in individuals with type-1 diabetes, as measured by the change from baseline in central corneal nerve fibre length (CNFL) at day 180.

Aim 2

To evaluate the effects of a six-month supplementation period with oral long-chain omega-3 PUFA supplements in individuals with type-1 diabetes on the change from baseline at day 180 for:

Key secondary outcomes:

Other corneal nerve structure and function parameters

[2 main variables for corneal nerve structure: central corneal nerve branch density (CNBD) and central corneal nerve fibre density (CNFD)

2 main variables for corneal nerve function: central corneal sensitivity thresholds to room and cooled temperatures]

Secondary outcomes:

- Patient-reported quality of life

[2 main variables: EQ-5D-5L VAS and Index]

- Small nerve fibre function

[6 main variables: CSP onset latency and duration in the upper limb, CSP onset latency and duration in the lower limb, QSART sweat volume and latency in the foot]

- Large nerve fibre function

[2 symptom/clinical sign composite score variables: MNSI and MDNS (clinical examination) scores]

[3 main neurophysiology variables: sural SNAP amplitude, peroneal motor conduction velocity and tibial minimum F-wave]

- Median nerve excitability

[8 main variables: Depolarising threshold electrotonus (TEd) (peak), TEd (90-100 ms), hyperpolarising threshold electrotonus (Teh) (90-100 ms), TEd (10-20 ms), superexcitability, subexcitability, resting current–voltage (I/V) slope, strength duration time constant]

Aim 3

To evaluate the safety of a six-month supplementation period with oral long-chain omega-3 PUFAs in individuals with type-1 diabetes, by evaluating the incidence of adverse events, change in habitual distance visual acuity, change in intraocular pressure, change in diabetic retinopathy grading, and change in blood pathology parameters from baseline at day 180.

3. Analysis sets/Populations

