- Continuous repeated measures data collected at more than one visit will be analysed using a constrained longitudinal data analysis technique (Liang 2000). The outcome (dependent variable) will consist of the baseline and postbaseline values. The model will assume a common baseline mean across the two treatment arms due to random allocation. It will incorporate time point (study visit) as a categorical variable, thus it will not assume a specific trajectory over time. In addition to study visit, the model will include treatment as the main factor and the treatment by study visit interaction. The variancecovariance among the repeated measurements will be defined as unstructured. In the case of non-convergence, we will consider alternative structures (first-order autoregressive, Toeplitz, compound symmetry). Using this model, study participants with a missing baseline or a missing postbaseline value will be included in the analysis but study participants with no outcome values will be excluded. This model will yield unbiased results when the outcome data are Missing At Random. We will report the estimate and two-sided confidence interval of the absolute difference between two treatment groups in the change from baseline to 3 months and 6 months postbaseline (if applicable). Before fitting this model, the distribution of the outcome will be explored. In addition, we will examine if there are potential violations of underlying model assumptions (e.g. residuals). As a result, we may apply an appropriate transformation (e.g. log-transformation) before fitting the final model.
- Binary data will be analysed using a logistic regression model. We will report
 the estimate and two-sided confidence interval of the odds ratio between the
 two treatment groups.
- Categorical data will be analysed using an ordinal logistic regression model.
 We will report the estimate and two-sided confidence interval of the odds ratio between the treatment groups.

Details of which model will be used for each of the primary, key secondary, and secondary outcomes can be found in Appendix 3.

Compliance

See Table 4 in **Appendix 4**.

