7.1.1 Multiple testing

The primary outcome at day 180 will be evaluated using the two-sided 5% level of significance.

Multiple testing for the key secondary outcomes related to corneal nerve parameters at day 180 will be assessed using the Benjamini-Hochberg stepwise method with a false discovery rate of 5% for: corneal nerve fibre density (CNFD), corneal nerve branch density (CNBD), central corneal sensitivity thresholds to room temperature, and central corneal sensitivity thresholds to cooled temperature. For these key secondary outcomes at day 180, we will report the multiplicity adjusted p-values.

For all other post-baseline time points and outcomes, we will report multiplicity unadjusted p-values. Given the large number of statistical tests, the probability of finding at least one false positive finding will be close to 100%. For this reason, we will exercise caution and in addition to p-values, associations will be interpreted based on the magnitude and direction of the association and width of the 95% confidence intervals.

All tests will be performed two-sided, and we will report two-sided 95% confidence intervals.

8. Sensitivity Analyses

Additional sensitivity analyses will be performed for the outcomes linked to the primary and key secondary aims for the following dataset:

- Dataset excluding participants deemed non-compliant (see definition in Section 6.3).

9. QC Plans

Source data verification of the data entered on REDCap was performed by the Principal Investigator (PI). Data was manually checked for accuracy from the source worksheets/original digital data record, for all participants, for the primary outcome (CNFL) and key secondary outcomes (CNFD, CNBD, central corneal sensitivity thresholds to room temperature, and central corneal sensitivity thresholds to cooled temperature). In addition, a subset of data comprising at least 20% of the full dataset,

was randomly selected by the PI for verification, to ensure that the observations and findings are recorded correctly and completely. Data found as incorrectly entered were verified against the original source documents, corrected on REDCap and recorded accordingly.

10. Programming Plans

A list of all planned tables and figures and their templates can be found in Appendix 4.

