Habitual distance visual acuity (LogMAR) - Right eye - Left eye								
Intraocular pressure (mmHg) - Right eye - Left eye								
Diabetic retinopathy in the worse eye, n (%) - None - Mild - Moderate - Severe - Proliferative								
Diabetic macular oedema in the worse eye, n (%) - None - Macular oedema - Clinically significant macular oedema								
Blood biochemistry								
HbAıC (mmol/mol)								
Cholesterol (mmol/L)								
HDL (mmol/L)								
LDL (mmol/L)								
Creatinine (µmol/L)								
Vitamin B12 (pmol/L)								
Folate (nmol/L)								

^{*} Mean and standard deviation unless stated otherwise.

[†] p-values are not adjusted for multiple testing.

Abbreviations: HbAıC, haemoglobin Aıc; HDL, high-density lipoproteins; LDL, low density lipoproteins.

Changes from the planned analysis in the Statistical Analysis Plan

- 1. A sensitivity analysis was performed for outcomes with substantial imbalance at baseline either in the mean (continuous outcomes) or geometric mean (log base e transformed outcomes) between groups. The imposed constraint of balance at baseline of the constrained longitudinal data analysis model was removed by adjusting the primary model for the interaction between baseline and treatment in addition to the factors already part of the longitudinal data analysis model.
- 2. We had intended to analyse categorical and binary variables using (ordinal) logistic regression analysis. However, this model could not be fitted due to the distribution of the data within and between groups. Instead, for categorical and binary variables, change from baseline at the study endpoint for each participant was categorised as negative change, positive change, or no change. Fisher's exact test was used to compare the proportions of participants between treatment groups. For MDNS scores, in changing from analysing this parameter as a continuous variable to a categorical variable, the class of neuropathy (class 0–3 as defined by the MDNS) was derived as the highest score from the clinical scoring or neurophysiology component.

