Data reported as the number of participants with the medications. Concomitant medications are categorised using the United States Pharmacopeia (USP; United States Pharmacopeial Convention) Drug Classifications 2019, published on https://www.usp.org/

Table S2. Compliance outcomes using systemic fatty acid profiles (Intention-To-Treat sample)

	0	mega-3 PUF	As		Placebo	Omega-3 PUFAs vs Placebo		
	Baseline (n=21)	Day 180 (n=21)	Change from baseline (n=21)	Baseline (n=22)	Day 180 (n=19)	Change from baseline (n=19)	Estimate (95% CI) (n =43)	p- value ^a
Omega-3 Index	4.9 (0.8)	8.2 (1.7)	3.3 (1.8)	4.6 (1.0)	4.8 (1.3)	0.12 (1.0)	3.3 (2.4,4.2)	< 0.001
EPA, %	0.6 (0.2)	2.11 (0.7)	1.5 (0.8)	0.6 (0.2)	0.7 (0.4)	0.08 (0.4)	1.4 (1.1,1.8)	< 0.001
DHA, %	1.9 (0.5)	3.0 (0.7)	1.1 (0.7)	1.8 (0.7)	1.8 (0.7)	0.01 (0.5)	1.1 (0.7,1.5)	< 0.001
Total omega-6, %	25.0 (4.7)	25.8 (3.4)	0.8 (4.1)	26.9 (2.8)	28.3 (2.6)	1.52 (4.0)	-2.1 (-3.9,-0.3)	0.023 b
Total omega-9, %	20.9 (5.0)	21.1 (2.5)	0.3 (5.6)	21.0 (3.8)	20.5 (1.9)	-1.26 (3.5)	0.7 (-0.7,2.0)	0.34
Omega- 6:omega-3 ratio	6.1 (1.7)	3.7 (0.9)	-2.4 (2.0)	7.2 (1.8)	7.3 (1.8)	0.2 (1.9)	-3.5 (-4.3,-2.6) ^c	<0.001°

Data are reported as mean and standard deviation. DHA=docosahexaenoic acid. EPA=eicosapentaenoic acid. PUFA=polyunsaturated fatty acid.

^a p-values are not adjusted for multiple testing.

^b In a sensitivity analysis adjusting for imbalance at baseline, the treatment effect for total omega-6 is -0.59 (-3.09,1.92) %; unadjusted p-value = 0.65.

^c In a sensitivity analysis adjusting for imbalance at baseline, the treatment effect for omega-6:omega-3 ratio is -2.54 (-3.77,1.32) %; unadjusted p-value <0.001.

Table S3. Safety outcome: Summary of adverse events (Safety sample)

	Omega-3 PUFAs (n=21)	Placebo (n=22)	Omega-3 PUFAs vs Placebo p- value
Summary of all adverse events ^a			value
At least one AE or SAE, n [%]	9 [43%]	7 [32%]	0.54
At least one AE, n [%]	9 [43%]	6 [27%]	0.35
At least one SAE, n [%]	0 [0%]	1 [5%]	1.0
Unrelated adverse events ^b			
Haematologic	0	1	
Ocular			
Posterior segment/retinal condition (not associated with diabetes)	0	2	
Light sensitivity/headache	1	2	
Respiratory symptoms	4	2	
Gastrointestinal (unrelated SAE)	0	1	
Musculoskeletal pain/cramping	1	1	
Change in blood glucose control	0	1	
Dermatological: rash or skin changes	2	0	
Cardiovascular: heart palpitations	1	0	
Immunologic: unrelated allergic reaction	1	0	
Potentially-related adverse events ^b			
Gastrointestinal: nausea ^c	2	1	

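### Table S3 compares adverse events between arms by p-value alone, although the SAP and its Table 5 shell call for an estimate with a 95% confidence interval

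*Combined protocol and SAP*

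**What the plan says.** Aim 3 (SAP section 2) is "To evaluate the safety of a six-month supplementation period with oral long-chain omega-3 PUFAs in individuals with type-1 diabetes". It lists adverse event incidence, visual acuity, intraocular pressure, retinopathy grading and blood pathology.

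For categorical data, SAP 6.2 (Statistical procedures) states: "We will report the estimate and two-sided confidence interval of the odds ratio between the treatment groups". The preceding bullet says the same for binary data. SAP 7.1.1 (Multiple testing) adds: "All tests will be performed two-sided, and we will report two-sided 95% confidence intervals". It also says results will be read from size, direction and interval width as well as p-values. The Table 5 shell in SAP Appendix 4 has an estimate and 95% CI column, and its rows include adverse events, retinopathy and macular oedema.

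Item 2 of the changes from the planned analysis reports that the logistic models could not be fitted. Each participant's change from baseline was classed as negative, positive or none, and "Fisher's exact test was used to compare the proportions of participants between treatment groups". No estimate or interval is named. Item 3, for the OSDI score, replaces a failed model with a Wilcoxon test and also names a Hodges-Lehmann estimate with a 95% CI.

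In Table S3 the row "At least one AE or SAE, n" (%) and the two rows below it show counts, percentages and a p-value. No between-arm estimate or interval is given.

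**The concern.** A p-value of 0.54 is easily taken to mean that the arms do not differ in adverse events. With 21 and 22 participants it says little about how large a difference could be. A safety aim asks what size of harm the data exclude, and only an interval answers that. Here the SAP had promised one, and the printed results for these rows leave it out.

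The graded outcomes raise a related problem. A Fisher test on three change categories responds to improvement as well as to worsening, so its p-value does not isolate harm. An estimate of the proportion worsening, with its interval, would.

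**Working it through.** **Inputs.** Table S3 (Safety sample, omega-3 n=21, placebo n=22): any AE or SAE 9 versus 7; any AE 9 versus 6; any SAE 0 versus 1. Alpha is 0.05 (protocol 8.1.3), two-sided (SAP 7.1.1).

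**Step 1: the printed p-values.** A two-sided Fisher's exact test gives:

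- 9/21 v 7/22: 0.537 (printed 0.54)
- 9/21 v 6/22: 0.347 (printed 0.35)
- 0/21 v 1/22: 1.0 (printed 1.0)

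All three agree, so Fisher's test was used for adverse events.

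**Step 2: the omitted risk differences.** Newcombe's interval combines the Wilson limits (l, u) of each proportion. With d = p1 - p2:

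- lower = d - sqrt[(p1 - l1)² + (u2 - p2)²]
- upper = d + sqrt[(u1 - p1)² + (p2 - l2)²]

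Wilson 95% limits:

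| Count | p | l | u |
|---|---|---|---|
| 9/21 | 0.429 | 0.245 | 0.635 |
| 7/22 | 0.318 | 0.164 | 0.527 |
| 6/22 | 0.273 | 0.132 | 0.482 |
| 0/21 | 0 | 0 | 0.155 |
| 1/22 | 0.045 | 0.008 | 0.218 |

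Any AE or SAE: d = 0.429 - 0.318 = 0.110.

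- lower = 0.110 - sqrt(0.184² + 0.209²) = -0.168
- upper = 0.110 + sqrt(0.206² + 0.155²) = 0.368

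Results for all three rows, omega-3 minus placebo:

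| Row | Risk difference | 95% CI |
|---|---|---|
| Any AE or SAE | +11 points | -17 to +37 |
| Any AE | +16 points | -12 to +41 |
| Any SAE | -5 points | -22 to +11 |

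For 0/21 SAEs the exact two-sided 95% upper limit is 1 - 0.025^(1/21) = 0.161, or 16%.

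**Step 3: is the planned odds ratio available?** The two main rows have no empty cell, so the unadjusted logistic odds ratio is the cross-product ratio.

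- Any AE or SAE: (9 × 15)/(12 × 7) = 1.61. The standard error of the log is sqrt(1/9 + 1/12 + 1/7 + 1/15) = 0.636, giving 95% CI 0.46 to 5.59.
- Any AE: (9 × 16)/(12 × 6) = 2.00, standard error 0.651, 95% CI 0.56 to 7.16.

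Only the SAE row has a zero cell, and Step 2 shows that limits exist there too.

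**Step 4: how little a non-significant p-value excludes.** Against 7/22 on placebo, 13/21 on omega-3 gives p = 0.069 and 14/21 gives p = 0.034, so significance needs 14 of 21 (67%). Assuming the true placebo rate equals the observed 7/22, summing over all tables gives Fisher's test 49.1% power for a doubling to 63.6%; it misses 51%. The result depends on the assumed placebo rate: power for a doubling is 25.7% from 20% and 71.8% from 40%.

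**The case against.** The strongest reply is that the plans specific to adverse events are descriptive. Protocol 7.3.1 and the SAP's adverse events section speak of tabulation, and Appendix 3 assigns no model to adverse events. Item 2 describes change from baseline, which does not fit an outcome such as having had at least one AE. Fisher's use there is known from the reproduced p-values and not from item 2's wording. This stands, and it makes the commitment to an adverse event odds ratio less explicit than for retinopathy. It does not remove the general text of SAP 6.2 and 7.1.1 or the Table 5 shell, which covers these rows. Once a between-arm test is printed, the promised interval belongs beside it.

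It is also true that the counts are printed, so a reader can derive the interval, and that the change of test is openly declared with a reason. The events thought possibly related were few (nausea, 2 versus 1).

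Three stronger readings are tempting and are not supported:

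- **That the whole safety aim rests on non-significance.** Aim 3 also covers visual acuity, intraocular pressure and blood pathology, planned with estimates and intervals. Table S10 prints them for the continuous blood measures. The documents contain no statement that the supplement was found safe.
- **That Fisher's test causes the low power.** It comes mainly from 43 participants in a trial sized on CNFL. Adding an interval does not change it.
- **That retinopathy and macular oedema were reported without an estimate.** Their results are not in these documents. The eGFR and ocular surface staining rows, which show p-values only, make it plausible but do not establish it.

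**Conclusion.** The point holds as a reporting gap in the adverse event comparison. Table S3 gives p-values where the SAP's general rules and the Table 5 shell call for an estimate and a 95% CI, and failure of the logistic model does not explain the omission. Both main point estimates are higher on omega-3, and the intervals reach +37 and +41 points, so a large excess is not excluded; nor is a moderate deficit.

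The intervals rest only on printed counts. The 51% miss rate also assumes that the observed 32% placebo rate is the true one, and should be read as illustration. For retinopathy and macular oedema the concern is limited to item 2's three-category test, which does not separate worsening from improvement.

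**What to change.** Keep Fisher's p-value, and amend item 2 so that it accompanies an estimate.

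- In the three summary rows of Table S3, add the risk difference (omega-3 minus placebo), or the planned odds ratio, with a score or exact 95% CI. For the zero-event SAE cell, add the exact upper limit.
- In the Table 5 rows, report the proportion in each arm whose retinopathy or macular oedema grade worsened, with the same estimate and interval.
- State that the adverse event part of Aim 3 is read from the interval and not from p>0.05, and that with 43 participants only large excesses can be excluded.

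The cost is a few lines of code and one extra column. No new data are needed. The wide intervals will be visible and the safety statement will be more modest.
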